3. OBJECTIVE AND OUTCOME MEASURES

OBJECTIVES	OUTCOMES	JUSTIFICATION FOR OUTCOMES
Primary		
To investigate whether delta-beta TMS to dlPFC-dSTR will produce an increase in goal-directed behavior during reward-based decision-making.	Behavioral metric, percentage of hard trials chosen, during the Streamlined Expenditure of Effort for Reward Task (S-EEfRT).	Stimulation is delivered prior to the decision epoch and the stimulation parameters were determined based on a previous study that investigated a different cognitive construct.
Secondary		
To investigate whether delta-beta TMS to dlPFC-dSTR will result in a lasting increase in delta-beta coupling during the decision epoch.	Neural metric, degree of phase-amplitude coupling between prefrontal delta oscillations and left motor beta oscillations, quantified during the decision epoch of the S-EEfRT.	Our previous study found increased delta-beta phase-amplitude coupling during the decision-epoch in participants with high goal-directed behavior.
Exploratory		
To investigate the degree to which traits of motivation predict individual differences in the impact of delta-beta TMS on goal-directed behavior.	Two-dimension factor analysis is run on clinical assessments to derive motivation and rumination personality dimensions. These scores are correlated with the impact of TMS on goal-directed behavior.	Our previous study found two symptom dimensions within participants with major depressive disorder that captured individual differences in reward-based decision-making. Here, we utilize personality assessments that might be similar to the clinical analog.
To investigate whether reward-evaluation is increased by theta-gamma TMS to medial PFC.	Behavioral metric of reward-evaluation is the percentage of hard trials chosen as a function of the incentive offered, during the S-EEfRT.	Our previous study found reward-evaluation was related to theta-gamma coupling. This additional behavioral metric allows for the investigation of the circuit- and cognitive-specificity of TMS.

OBJECTIVES	OUTCOMES	JUSTIFICATION FOR OUTCOMES
To investigate whether theta-gamma coupling is increased by theta-gamma TMS to medial PFC.	Neural metric, degree of phase-amplitude coupling between prefrontal theta oscillations and posterior parietal gamma oscillations, quantified during the decision epoch of the S-EEfRT.	Our previous study found increased theta-gamma phase-amplitude coupling during the decision-epoch in participants with high reward-evaluation behavior.
To investigate whether functional connectivity between dorsal striatum and left lateral prefrontal cortex predicts individual differences in the impact of delta-beta TMS on goal-directed behavior.	Functional connectivity analysis of resting-state functional MRI is correlated with the impact of delta-beta TMS on goal-directed behavior.	Previous research has suggested that frontal-striatal connectivity is related to reward-based decision-making. Participants with reduced connectivity within this neural circuit may be predictive of the impact of TMS on reward-based decision-making.

4. STUDY DESIGN

4.1 OVERALL DESIGN

This study is a pilot, four-session, crossover study with transcranial magnetic stimulation (TMS), electroencephalography (EEG), and magnetic resonance imaging (MRI) to understand the causal role of delta-beta coupling in goal-directed behavior in the dorsolateral prefrontal cortex (dIPFC) to dorsal striatum (dSTR) circuit. Participants that request to be in the experiment will provide verbal, documented consent to undergo a phone screening to assess that the participant meets initial exclusion/inclusion criteria. Participants complete an MRI and TMS screening form over the phone to ensure eligibility.

The first session will be an EEG session with the reward-based decision-making task. At the start of the session, we will acquire written informed consent. Then, we will administer a pregnancy test if applicable. Participants will complete a five assessments: the Snaith Hamilton Pleasure Scale (SHAPS) (Snaith et al. 1995), Behavioral Activation System and Behavioral Inhibition System (BIS/BAS) (Carver and White 1994), Temporal Experience of Pleasure Scale (TEPS) (Gard et al. 2006), the State-Trait Anxiety Inventory (STAI) (Spielberger 2010), and Ruminative Responses Scale (RRS) (Nolen-Hoeksema, Larson et al. 1999). Note that our participants are from a convenient sample and are not required to be diagnosed with major depressive disorder. Thus, these assessments were selected as they survey various personality traits that might be relevant to performance in the task. In our previous published study using this task, we discovered a continuum of task performance between the control participants and the participants within a major depressive disorder (Riddle et al. Cerebral Cortex 2022). We speculate that participants with personality traits related to reduced behavioral approach (quantified by the BIS/BAS) could be a precursor to symptoms of anhedonia (quantified by the TEPS and SHAPS). Similarly, increased personality traits of behavioral inhibition (quantified in the BIS/BAS) could be a precursor to symptoms of anxiety (STAI and RRS). Thus, we collect this data in healthy control participants as an exploratory aim of the study.

The scalp dimensions of each participant are calculated and a low-profile EEG net is applied. For each session, muscle activity from the hand and forearm are recorded. Next, the participants complete an eyes-open and eyes-closed resting-state recording of EEG. Then, the streamlined version of the Expenditure of Effort for Reward Task (S-EEfRT) is completed. These data serve as baseline measurement of brain activity without any form of stimulation. This session takes approximately 1.5 hours to complete. After each block of the task, the task difficulty will increase or decrease based on performance. At the end of the session, if the participant chose to perform the HARD task greater than 85% of the time or less than 15% of the time, then the participant will not be invited to the next session of the experiment. The rationale is that we are studying reward-based decision-making and participants that do not dynamically change their response based on the incentive are not engaged with the relevant cognitive constructs under investigation in this study.

For the second session, participants are instructed to arrive at the Biomedical Research Imaging Center (BRIC) in Marsico Hall on UNC-CH campus. In the 24 hours prior to this session, participants complete an MRI screening form. This screening form is the standard provided by the BRIC. During the phone screening, if there is any ambiguity in the eligibility of the participant, then we consult with the technicians at the BRIC for approval to conduct an MRI. Then, in the 24 hours prior to their MRI session, MR technicians at the center review a new screening form and confirm their eligibility to receive an MRI. Because this is the same form used in the screening for the experiment, the only way that a participant would fail to be eligible at this stage is if there was some change in their eligibility between sessions. While this is highly

unlikely, the participant would be discontinued from participating. Participants are instructed to arrive at the facility 30 minutes before the start of the scheduled MRI block to ensure that they are ready to go into the MRI for the 60-minute allotted timeslot. During the 60 minutes of scanning, a 5-minute structural MR is acquired and the remaining time is used to complete as many blocks of the EEfRT as possible. The minimal number of sessions required to use the data is 5 blocks, which requires approximately 25 minutes to collect. Note that the only other scan of significant length acquired during this time is a 5-minute anatomical scan and the remaining 50 minutes or more is dedicated to acquisition of the task data that is used for localization. Thus, we do not expect to collect less than 5 blocks of data in any given participant. However, if a participant was unable to complete the requisite number of sessions, then they would be excluded from the rest of participation. We expect that this is a highly unlikely. Functional MRI data is analyzed before the 3rd and 4th session to localize the regions of dorsolateral PFC and medial PFC for stimulation. In our analysis, we will draw a region of interest mask in the head of the left caudate (dSTR) and in left nucleus accumbens (vSTR) and localize the region in dlPFC and mPFC with peak functional connectivity in task-based functional connectivity to these regions. In our pilot data, we found that the contrast of HARD vs EASY localized the anterior middle frontal gyrus and the contrast of HIGH vs LOW incentive localized the super frontal junction. Thus, we will choose regions in these anatomical areas with maximal connectivity to their respective nucleus in the striatum.

The order of regions (dlPFC then mPFC, or mPFC then dlPFC) targeted by TMS in the third and fourth session will be randomized and counter-balanced. First, the participants will be fitted with a low-profile EEG net and EMG electrodes to the hand and forearm. For the third and fourth session, the same stimulator intensity will be used as in the first session. The structural MRI and regions of interest (dlPFC and mPFC) are imported into Localite neuronavigation software. The participant wears a 3D stereotaxic tracking headband and is registered to their structural MRI. Then, the TMS coil is targeted to either mPFC or dlPFC and the position of the coil relative to the head is recorded throughout the session. The participant performs the S-EEfRT as the patterned trains of TMS are delivered on every trial. Each block of the study is randomized to receive either delta-beta patterned (triplets of TMS pulses at 20 Hz every 3Hz), theta-gamma patterned (triplets of pulses at 50 Hz every 5 Hz), or an arrhythmic pattern (same number of pulses and duration with a random inter-pulse interval). After stimulation, a questionnaire is provided with common side effects of TMS. Based on the results of the stimulation side effects questionnaire, a structured adverse events interview is conducted to acquire more information regarding any side effects that were selected to be “very high” by the participant. This session will take approximately 2 hours.

4.2 SCIENTIFIC RATIONALE FOR STUDY DESIGN

This study is a fully crossed target engagement study. It is not possible to include blinding in the study for either the participant or the experimenter. The difference between the active control pattern of TMS and the targeted pattern of TMS as well as the difference between dorsolateral PFC and medial PFC will not be meaningfully discernible to the participant as there is a difference of only a few centimeters between sites and only a fraction of a second for the stimulation patterns. There is no obvious association between the site of stimulation and the frequency of stimulation and the task itself. Therefore, not only is blinding

not possible, but it is not necessary for the scientific questions under investigation in this study. In a recent review by Duecker and Sack *Frontiers in Psychology* 2015, the authors survey modern approaches to creating a sham form of TMS. These efforts have been unsuccessful despite increasingly sophisticated designs. The authors found that even with moderate success in blinding in a parallel arm study where the participant is naïve to stimulation, when a design is crossover, the participants become aware that the stimulation is placebo. These observations lead to the conclusion that even when sham stimulation is used, the experiment should include an active control condition such as an alternate location of stimulation or an alternate frequency of stimulation: “TMS experiments always require an active TMS control condition, and sham TMS approaches can never be sufficient as they fail to demonstrate such specificity” (Duecker and Sack 2015).

Furthermore, the experimenters cannot be blinded to the site of stimulation as this needs to be carefully maintained throughout the experiment using neuronavigation, nor to the frequency of stimulation as these are audible to the experimenter. The primary and secondary outcome of the study include a control condition within each session and within a participant between sessions. Thus, the scientific integrity of the study is provided through multiple control conditions built into the crossover experimental design: spatial variable (dIPFC vs mPFC), temporal variable (delta-beta vs theta-gamma vs arrhythmic), and cognitive variable (goal-directed behavior vs reward evaluation). Our previous study found that goal-directed behavior was positively correlated with delta-beta coupling and reward-evaluation was positively correlated with theta-gamma coupling (Riddle et al. *Cerebral Cortex* 2022). Thus, this preliminary data provides a strong motivation for the type of stimulation used in this experiment. In addition, our previous study discovered a significant negative relationship between symptoms of anhedonia in major depressive disorder with goal-directed behavior and delta-beta coupling. Thus, this study will serve as a critical target engagement study such that future studies may use these results to develop interventions to treat symptoms of anhedonia in MDD.

[figure not shown]
Finally, our exploratory outcomes hypothesize that theta-gamma stimulation to medial PFC will increase reward-evaluation during the task. Thus, all conditions of the experiment are of importance to the outcome of the experiment. Therefore, the experimenter will not be unconsciously biased towards one session or another because all of them are important to the success of the project. In addition, the type of stimulation for each block of the task is randomized and not known to the participant or experimenter until the start of the block. Thus, the experimenter will not be able to bias the experiment in any way because they are blind to the experimental condition during the slight adjustments that occur during each block. Furthermore, the experimenter does not converse with the participant during the task and the task is computerized such that there are minimal human interactions that could bias the participant one way or another. In addition, the behavioral metrics of interest are patterns of decision-making within the same task condition. Thus, a hypothetical unconscious systematic bias would have to influence a particular pattern of behavior on a particular block of the task but not others within the same session. This type of influence is highly unlikely, if not nearly impossible, given our experimental design.

4.3 JUSTIFICATION FOR DOSE

Transcranial magnetic stimulation (TMS) is a safe, non-invasive, widely-used tool that applies focal electric fields to the brain using magnetic coils placed on the scalp (Rossi et al. 2009). On the first stimulation session of the study, participants will receive a motor thresholding procedure in which electrodes are attached to the first dorsal interosseous muscle of the right hand, or another muscle on the hand or arm that is accessible to be targeted by TMS to the motor cortex. The contralateral motor cortex will be targeted by single pulses of TMS with increased

stimulator output until a motor evoked potential (MEP) is generated: defined as a near-instantaneous increase muscle activity greater than 200 microvolts. Next, the intensity of single pulse TMS will be lowered until a MEP is generated on five out of ten pulses. This is defined as the motor threshold for the participant (Rossi et al. 2009). If the motor threshold cannot be determined via MEP, the experimenter will use visible twitches instead of MEP. Participants will receive 15 pulses of patterned TMS at 80% of their motor threshold during every trial. Patterned TMS takes three different forms (Figure 2). Delta-beta TMS delivers bursts of three pulses at 20 Hz (50 millisecond inter-pulse interval) with an inter-burst interval of 3 Hz (167 milliseconds). Theta-gamma TMS delivers bursts of three pulses at 50 Hz (20 millisecond inter-pulse interval) with an inter-burst interval of 5 Hz (200 milliseconds). As a control for the frequency-specificity of patterned TMS, arrhythmic TMS is delivered with a randomized inter-pulse intervals that are generated for each trial. The duration of arrhythmic TMS is randomly selected from a uniform distribution between the duration of delta-beta and theta-gamma TMS. The minimum inter-pulse interval will be 20 milliseconds. Between every train will be at least 11 seconds. An inter-train-interval of 11 seconds or greater allows for any residual effects of stimulation to return to baseline. This intensity, inter-pulse-interval, and inter-train-interval is well within the safety guidelines set forth for repetitive TMS (Wassermann, 1998; Rossi et al., 2009) and has been used in similar paradigms as the one described here. For example, Hermiller et al. 2020 delivered two seconds of theta-gamma patterned TMS (30 pulses per trial) at 80% of motor threshold (Hermiller et al. 2020). In addition, many other studies have delivered trains of TMS at higher intensities, upwards of 120% of motor threshold, on every trial of a cognitive task (Thut et al. 2011; Hanslmayr et al. 2014; Albouy et al. 2017)(Riddle et al. 2019; Riddle et al. 2020c; Sauseng et al. 2009). During a TMS session, participants will complete six blocks of 30 trials each. The participant will receive stimulation in either delta-beta, theta-gamma, or arrhythmic in a blocked design (the same stimulation is delivered for every trial in a block). The sequence of blocks will be randomized and counterbalanced such that each participant received each condition of TMS for 60 trials total. The third and fourth session of the experiment will be both be TMS sessions, where TMS is delivered to either the dorsolateral prefrontal cortex (dlPFC) or to medial prefrontal cortex (mPFC). The order and TMS sites will be randomized and counterbalanced across participants. Thus, at completion of the full experiment, participants will have received 12 blocks of 30 trials each of stimulation (180 trials per TMS session). In addition, two abbreviated blocks of TMS to mPFC and dlPFC will be administered at the end of the first session to assess for tolerability of TMS.

The evoked electric field from stimulation will be simulated using finite-element modeling of the neuroanatomical MRI for each participant (Gomez, Dannhauer, Peterchev *Neuroimage* 2021). This method ensures that the evoked stimulation strength is within a safe level beyond standard stimulation methodology. The time between each

patterned-train will be a minimum of 11 seconds. These stimulation parameters for individual trains and time between trains fall within the safety guidelines set forth by the Rossi et al., *Clin Neurophysiol* 2009 “The Safety of TMS Consensus Group: Safety, ethical considerations, and application guidelines for the use of transcranial magnetic stimulation in clinical practice and research”, which has guided TMS research the past decade (Rossi et al. 2009). Last year, these guidelines were re-affirmed with an updated safety review (Rossi et al. 2020). The longer the time between each train the better the safety profile from stimulation. Furthermore, patterned stimulation such as the theta-gamma burst pattern, used as a control frequency in this proposal, has been extensively investigated for its safety profile. A meta-analysis conducted by Oberman et al. *J Clin Neurophysiol* 2011 concluded that patterned TMS trains present only a minimal seizure risk with a single case of seizure out of 4,500. The participant was healthy and the protocol used was continuous theta-burst delivered at 100% of motor threshold to motor cortex. Thus, our use of 80% of motor threshold and targeting of dorsolateral and medial prefrontal cortex (less excitable regions of the brain) further reduces the risk. The safety of a TMS train is defined by the inter-pulse interval, with a short inter-pulse interval presenting higher risk (Rossi et al. 2009; Rossi et al. 2020). Thus, the novel delta-beta pattern (3 Hz by 20 Hz) proposed in this study is most likely safer than the theta-gamma pattern (5 Hz by 50 Hz). Finally, we will be delivering 180 trains of 5 bursts each and each train is separated by a considerable amount of time (minimum of 11 seconds) with time for self-paced breaks between every block in the experiment. Thus, this number of pulses exceeds the typical number of bursts in a continuous theta-burst protocol but the overall delivery time is considerably longer. Of note, recent experiments using accelerated-intermittent theta-burst TMS deliver up to 10 trains of intermittent theta-burst per day for many consecutive days. A recent investigation of accelerated-intermittent theta-burst TMS that delivered iTBS 10 times per day with each iTBS train consisting of 1,800 pulses for 5 consecutive days: 18,000 pulses per day at 90% motor threshold, 90,000 pulses in one week (Cole et al. *Am J Psychiatry* 2020). Our proposal to deliver 900 bursts (180 trains of 5 bursts) over the course of 1.5 hours with 11 seconds between train is well within current safety considerations.

To further reduce risk during the stimulation session, the participant will be actively monitored by the researcher and any signs of duress will result in a termination of stimulation and the experimental session. There is a rare likelihood that the participant could undergo a seizure from stimulation. While this is unlikely, all of our researchers are trained in first-aid and CPR with (RedCross certificate). In addition, a collaborator of the Carolina Center for Neurostimulation, [name], is an epileptologist in the Department of Neurology that is on-call for emergencies and her contact information is posted in our experiment rooms. All researchers are trained in the Carolina Center for Neurostimulation in how to respond in the event of a seizure and are instructed in best monitoring practices to prevent its occurrence. This is a known, unlikely risk of TMS and our screening procedure was developed according to established guidelines (Rossi et al. 2009; Rossi et al. 2020) to prevent participants from receiving TMS that have contraindications.

Finally, there is a theoretical risk that TMS may damage hearing over prolonged exposure given the proximity of the stimulator to the ears (Rossi et al. 2009; Rossi et al. 2020). Thus, we provide participants with ear plugs during motor threshold stimulation and with EEG-compatible ear-buds with an inflatable foam shape during task performance with TMS. These ear buds provide noise protection by making a tight seal and contain a small tube so that we can play white noise to the participant to help mask the noise of the stimulation for analysis purposes. In addition, the experimenter wears ear plugs during TMS to protect their hearing.

EEG and EMG will be collected using the Geodesic 400 system (EGI INC., Eugene, OR, USA). Collecting simultaneous EEG and EMG with TMS does not pose any additional risk over TMS on its own. EEG and EMG do not involve brain stimulation and is used purely for electrophysiology (minimal risk).

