Outcomes:	
Primary Outcome: Behavioral metric, percentage of hard trials chosen, during the streamlined version of the Expenditure of Effort for Reward Task (S-EEfRT).
 
Secondary Outcome: Neural metric, degree of phase-amplitude coupling between prefrontal delta oscillations and left motor beta oscillations, quantified during the decision epoch of the S-EEfRT.
 
Exploratory Outcome 1: Personality metric, traits of motivation explain individual differences in the primary outcome.
 
Exploratory Outcome 2: Behavioral metric, percentage of hard trials chosen as a function of incentive during the S-EEfRT.
 
Exploratory Outcome 3: Neural metric, degree of phase-amplitude coupling between prefrontal theta oscillations and posterior gamma oscillations, quantified during the decision epoch of the S-EEfRT.

	Exploratory Outcome 4: Connectivity metric, strength of task-based functional MRI connectivity between dorsal striatum and dorsolateral prefrontal cortex during the decision-epoch of the S-EEfRT.
Study Population:	We will recruit healthy men and non-pregnant women ages 18-65 without a neurological disorder, free of benzodiazepines and anticonvulsant medications. Participants must also be eligible to receive rTMS and MRI. Participants will be recruited from the Chapel Hill, Durham and Raleigh areas.
Phase:	Pilot Phase
Description of Sites/Facilities Enrolling Participants:	University of North Carolina at Chapel Hill
Description of Study Intervention:	We will use the MagPro X100 or R30 system (MagVenture Inc., Alpharetta, Georgia, USA) for transcranial magnetic stimulation. The MagPro X100 or R30 are an advanced, high performance magnetic stimulator designed primarily for research purposes. It is a high-quality tool for researchers with a large choice of stimulating parameters and has stimulation rates up to 100 pulses per second at high intensities and the possibility to combine waveforms and pulse modes. Patterned rhythmic TMS will be delivered in either cross-frequency delta-beta, cross-frequency theta-gamma, or an arrhythmic pattern that is matched for the number of pulses and duration. Stimulation will be delivered at 80% of motor threshold in the 2 seconds before the decision epoch with 5 triplets of 3 pulses per train per trial.
Study Duration:	2 years

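### Section 4.3 equates a delta-beta inter-burst interval of 3 Hz with 167 ms; the two differ by a factor of two, and no reading of the interval fits both rhythmic patterns

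*Combined protocol and SAP*

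**What the plan says.** Section 4.3 (Justification for Dose) specifies the two rhythmic patterns in adjacent sentences. Delta-beta is three pulses at 20 Hz, 50 ms apart, "with an inter-burst interval of 3 Hz (167 milliseconds"). Theta-gamma is three pulses at 50 Hz, 20 ms apart, "with an inter-burst interval of 5 Hz (200 milliseconds").

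Elsewhere the slow figures are used as burst repetition rates. Section 4.1 has "delta-beta patterned (triplets of TMS pulses at 20 Hz every 3Hz") and "theta-gamma patterned (triplets of pulses at 50 Hz every 5 Hz"). Later in Section 4.3 the protocol refers to "the novel delta-beta pattern (3 Hz by 20 Hz) proposed in this study" and judges it "most likely safer than the theta-gamma pattern (5 Hz by 50 Hz"). So 3 Hz appears three times and 167 ms once.

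Two other statements depend on this timing. The Synopsis places stimulation "in the 2 seconds before the decision epoch with 5 triplets of 3 pulses per train per trial". Section 4.3 sets the control condition from the two rhythmic trains: "The duration of arrhythmic TMS is randomly selected from a uniform distribution between the duration of delta-beta and theta-gamma TMS".

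**The concern.** The slow rhythm is what makes the delta-beta condition a delta condition, and the primary and secondary hypotheses both rest on it. Section 4.3 is the only place in the available text that gives the interval in milliseconds, and there the two expressions of the same quantity disagree twofold. Two people working from that paragraph could program different delta-beta trains. Since the arrhythmic duration is bounded by the delta-beta duration, they would program different control trains as well.

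The worst case is conditional. If, and only if, bursts were delivered 167 ms apart from onset to onset, the slow rate would be about 6 Hz. That lies outside both delta bands in the protocol (2-4 Hz in Section 2.2, 2-3 Hz in Section 9.4.3) and close to the 5 Hz comparator. The secondary outcome would then measure coupling to a phase band that was not the stimulated rate. The documents do not show that this happened.

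**Working it through.** **Inputs.** Delta-beta: 3 pulses, 50 ms apart, so 100 ms from first to last pulse; interval given as 3 Hz and as 167 ms (Section 4.3). Theta-gamma: 3 pulses, 20 ms apart, so 40 ms from first to last pulse; interval given as 5 Hz and as 200 ms (Section 4.3). Five bursts per train (Synopsis).

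**Step 1: the protocol's own conversions, by 1,000/f.**
- 1,000/20 = 50 ms, as stated.
- 1,000/50 = 20 ms, as stated.
- 1,000/5 = 200 ms, as stated.
- 1,000/3 = 333 ms, against 167 ms stated. In reverse, 1,000/167 = 5.99 Hz. The ratio is 333.3/167 = 2.00.

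Three of the four figures reproduce exactly and the fourth does not.

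**Step 2: other meanings of the interval.** Each reading has to work for both patterns.
- *Silent gap, last pulse to next first pulse.* Delta-beta: 1,000/(100 + 167) = 3.75 Hz. Theta-gamma: 1,000/(40 + 200) = 4.17 Hz. Neither matches.
- *Gap after a full burst slot of three inter-pulse intervals.* Delta-beta: 1,000/(150 + 167) = 3.15 Hz. Theta-gamma: 1,000/(60 + 200) = 3.85 Hz, not 5 Hz.
- *Half cycle.* 500/3 = 166.7 ms matches delta-beta, but 500/5 = 100 ms, not the 200 ms stated for theta-gamma.

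**Step 3: what follows for the trains.** Duration from first to last pulse is 4 × onset spacing + burst length:
- 3 Hz and 5 Hz as onset spacing: 4 × 333.3 + 100 = 1,433; 4 × 200 + 40 = 840.
- 167 and 200 ms as onset spacing: 4 × 167 + 100 = 768; 840 as before.
- Silent gap: 4 × 267 + 100 = 1,168; 4 × 240 + 40 = 1,000.
- Burst slot: 4 × 317 + 100 = 1,368; 4 × 260 + 40 = 1,080.

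| Reading | Delta-beta / theta-gamma slow rate (Hz) | Delta-beta train (ms) | Theta-gamma train (ms) | Arrhythmic range (ms) | Width (ms) |
|---|---|---|---|---|---|
| 3 Hz and 5 Hz as onset spacing | 3.00 / 5.00 | 1,433 | 840 | 840-1,433 | 593 |
| 167 and 200 ms as onset spacing | 5.99 / 5.00 | 768 | 840 | 768-840 | 72 |
| Silent gap | 3.75 / 4.17 | 1,168 | 1,000 | 1,000-1,168 | 168 |
| Gap after burst slot | 3.15 / 3.85 | 1,368 | 1,080 | 1,080-1,368 | 288 |

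The gap rows apply the same reading to both patterns. If the silent gap is applied to delta-beta only and theta-gamma stays at 5 Hz, the arrhythmic range is 840-1,168 ms. Every train is shorter than the 2,000 ms window in the Synopsis, so that window cannot decide between the readings.

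**Step 4: does the planned ANOVA protect against this?** With DB, TG and AR for the three stimulation types, and d and m for dlPFC and mPFC, the site-by-type interaction in Section 9.4.2 is

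(DBd − ARd) − (TGd − ARd) − [(DBm − ARm) − (TGm − ARm)] = DBd − TGd − DBm + TGm.

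The arrhythmic terms cancel, so the control's duration does not enter the interaction. The delta-beta terms remain, so the interaction gives no protection if the delta-beta condition itself is mistimed.

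**The case against.** The strongest reply is that this is a slip in one parenthesis. The 3 Hz figure appears three times and consistently, 167 ms appears once, and 167 ms is exactly half a 3 Hz cycle, which makes a one-off conversion error plausible. The burst-slot reading also gives 3.15 Hz, which rounds to 3, so for delta-beta alone it does not clash with the rates quoted elsewhere. Section 4.3 refers to Figure 2 for the patterns. That figure is not available here and may settle the matter for a reader of the full protocol. Finally, alpha, power, sample size, the endpoint definition and the ANOVA are untouched, and the protocol's safety argument about trains rests on the inter-pulse interval, which is not in dispute.

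Much of this stands. A text slip is plausible, the 6 Hz scenario is hypothetical, and the gap readings are shown only to demonstrate that they fail. But the half-cycle and burst-slot readings each fit delta-beta by breaking the theta-gamma figure in the next sentence, so neither explains the text. A plausible slip is also not evidence of what was programmed. The number of times each value is repeated cannot show that; only the stimulation timing can.

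**Conclusion.** The contradiction holds with high confidence and should be fixed before analysis. It needs no outside figure: the two values in one phrase differ by a factor of 2.0 under the conversion the section uses everywhere else, and no single reading fits both rhythmic patterns. Following one value or the other gives a five-burst delta-beta train of 1,433 or 768 ms, and an arrhythmic range 593 or 72 ms wide. These durations assume five bursts per train, measured from first to last pulse, with onset-to-onset spacing. What was actually delivered is unknown from the documents, and no view is taken on which value was intended.

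**What to change.** - Reconcile Sections 4.1 and 4.3 so that the delta-beta frequency and the millisecond interval agree wherever they appear.
- State whether the inter-burst interval means onset-to-onset spacing or a gap, for both rhythmic patterns.
- Confirm the programmed or delivered timing against the reconciled text before the data are analysed.

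A minor, separate point for the same edit: the Synopsis and Section 4.1 describe the arrhythmic train as having the same duration as the rhythmic ones, whereas Section 4.3 draws it uniformly between the two rhythmic durations. Align the wording. Add a sentence that each rhythmic-minus-arrhythmic contrast, read alone, mixes rhythm with train duration. The mean difference is half the range width: 593/2 = 297 ms under 3 Hz and 5 Hz onset spacing (delta-beta longer, theta-gamma shorter), and 72/2 = 36 ms in the opposite direction under 167 and 200 ms onset spacing.

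The cost is wording in a few places and one timing check. The design, the sample size and the planned ANOVA stay as they are.
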